Assessing the significance of some biomarkers in perioperative period after thoracic aortic reconstruction

NCT04689139 Protocol ID039420200002

Date 22.12.2020

Objective. This study aims to assess the association between levels of biomarkers and postoperative complications in patients after thoracic and thoracoabdominal aortic reconstruction.

Design. Single group assessment observational open label study.

Methods. The study protocol approved by the Ethics Committee. Patients included: ascending aortic and aortic arch reconstruction.

Eligibility. Age 18-75 years. Inclusion Criteria: Elective thoracic and thoracoabdominal surgery. Exclusion Criteria: Hemolysis in blood sample.

The concentrations of proadrenomedullin, procalcitonin, presepsin, procalcitonin, troponin I and N-terminal brain natriuretic peptide measurement before induction anesthesia, at the end of the surgical operation and in 6 hours after surgery.

Turnaround time test no more than 40 minutes. The concentrations of procalcitonin and proadrenomedullin determined on a Kryptor Compact Plus analyzer (Thermo Fisher Scientific), troponin I, NT-proBNP and presepsin on a PATHFAST analyzer (LSI Medience Corporation).

Statistical analysis. The normality of the distribution estimated by chi square. The data analyzed with a non-parametric test (Mann–Whitney U-test) and Student t-test according to normality tests. A P value ≤ 0.05 considered to be statistically significant. ROC-analysis to identify the predictors of postoperative complications and regression coefficients for odds ratio calculation for each dependent variable. Regression analysis to assess the influence on quantitative variables of biomarkers.

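### The only decision rule is P ≤ 0.05, while up to 15 marker-time candidates per complication are searched for predictors with no predictor criterion, multiplicity rule, exploratory label or internal validation

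*Combined protocol and SAP*

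**What the plan says.** The Objective is broad: "This study aims to assess the association between levels of biomarkers and postoperative complications". The Design is "Single group assessment observational open label study".

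The measurement paragraph lists the markers: "The concentrations of proadrenomedullin, procalcitonin, presepsin, procalcitonin, troponin I and N-terminal brain natriuretic peptide measurement". Procalcitonin is printed twice, so the six entries are five different markers. Sampling is before induction, then "at the end of the surgical operation and in 6 hours after surgery", which makes three times.

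The Statistical analysis section first describes group comparisons: "The data analyzed with a non-parametric test (Mann–Whitney U-test) and Student t-test according to normality tests". The threshold follows: "A P value ≤ 0.05 considered to be statistically significant". The next sentence reads "ROC-analysis to identify the predictors of postoperative complications and regression coefficients for odds ratio calculation for each dependent variable". A last sentence adds a regression analysis for quantitative variables.

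The document does not:
- list the complications, or name a primary complication, biomarker or time point;
- say how the three times enter the analysis;
- say what makes a marker a predictor;
- mention a multiplicity rule, an exploratory label, or any validation or optimism correction.

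**The concern.** A reader who meets a 5% threshold will take it that an uninformative marker has about a 5% chance of being named. That holds for one test fixed in advance. Here several markers at several times are screened against each complication, and the ones that stand out may be reported as predictors. The chance that something stands out is then well above 5%.

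There is a second effect. If the best marker is picked, and its AUC and cut-off are reported from the same patients, both are too favourable even when nothing is there. A chance finding could then be presented as a usable perioperative predictor with a specific cut-off. Because the criterion is not stated, it could also be settled after the data are seen, and the false-predictor rate depends heavily on which one is used.

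**Working it through.** The plan gives no sample size, power or family-wise error figure, so there is nothing of its own to reproduce.

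**Inputs from the document.** Threshold 0.05; five distinct biomarkers; three times. This gives 5 × 3 = 15 candidates per complication, or five if each marker enters once.

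**Assumptions.** Two-sided tests; no marker informative; one complication; P ≤ 0.05 marks a predictor. The correlations, and the sizes of 100 patients with 25 events and 60 with 15, are also assumed.

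**Step 1: independent tests.** The chance of at least one P ≤ 0.05 among m tests is 1 − 0.95^m.
- m = 15: 1 − 0.95^15 = 53.7%
- m = 5: 1 − 0.95^5 = 22.6%

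**Step 2: correlated tests.** Repeated samples of one marker, and different markers in one patient, will be correlated, which lowers these rates. The 15-candidate rows below are rank tests on simulated null data (100 patients, 25 events, 10,000 replicates). The five-candidate rows are simulated normal test statistics.

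| Candidates | Assumed correlation | At least one false P ≤ 0.05 |
|---|---|---|
| 15 | within/between biomarker 0.5/0.2 | 46% |
| 15 | 0.7/0.3 | 40% |
| 15 | 0.9/0.5 | 29% |
| 15 | 0.95/0.8 | 18% (17% with normal test statistics) |
| 5 | between biomarker 0.5 | 18% |
| 5 | 0.7 | 15% |
| 5 | 0.8 | 13% |
| 5 | 0.9 | 10% |

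Relative to 5%, the span is 10.1/5 ≈ 2 to 53.7/5 ≈ 11 times.

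**Step 3: other possible criteria.** These use 15 candidates, with correlations from independence to 0.95/0.8.
- AUC of at least 0.70 in either direction: 1-4% at 100/25, but 9-26% at 60/15.
- Odds-ratio P ≤ 0.05 from one-marker logistic models: 17-50% at 100/25.
- AUC 95% CI excluding 0.5 (DeLong): 21-59% at 100/25. The top exceeds 53.7% because this interval is itself somewhat too narrow at this size (about 6% error for a single test). That part is not multiplicity.

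**Step 4: selection optimism.** At correlations 0.5/0.2 the best of 15 null AUCs, in either direction, averages 0.63 (100/25) or 0.67 (60/15). The true value is 0.50. The Youden index (sensitivity + specificity − 1) at the cut-off chosen for that marker averages 0.29 or 0.37, when the true value is 0.

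**Step 5: does correction work?** Marker, direction and cut-off selection were repeated in every resample (400 null replicates, correlations 0.5/0.2).

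| Setting | Measure | Apparent | Bootstrap | Repeated 5-fold CV | True |
|---|---|---|---|---|---|
| 100/25 | AUC | 0.631 | 0.540 | 0.497 | 0.500 |
| 60/15 | AUC | 0.671 | 0.559 | 0.502 | 0.500 |
| 100/25 | Youden | 0.287 | 0.097 | −0.007 | 0 |
| 60/15 | Youden | 0.369 | 0.139 | 0.000 | 0 |

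For AUC the bootstrap leaves 0.040/0.131 = 31% and 0.059/0.171 = 35% of the optimism. For the Youden index it leaves 0.097/0.287 = 34% and 0.139/0.369 = 38%. Cross-validation leaves essentially none, but its estimates are more variable.

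**The case against.** The strongest reply is that this is an observational single-group study of association. Such a study may properly look at several markers without multiplicity control, and requiring a single primary would be a design preference. That stands, and the fix does not require one. It does not remove the gap, though: the plan never calls itself exploratory, and it sets a significance threshold beside a stated search for predictors.

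Second, a reader might infer that the plan defines a predictor by P ≤ 0.05, and so carries a better-than-even chance of a false one. The document does not support this. The threshold follows the group-comparison sentence, and the ROC sentence has no criterion at all. With AUC ≥ 0.70 at 100/25 the rate would be only 1-4%. The regression sentences could also mean one multi-marker model per complication, a reading not simulated here.

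Third, the 54% needs three samples of one marker around one operation to be independent, which is unlikely. Nor is there a firm lower limit. Whether there are five or 15 candidates is a choice the plan leaves open, whereas correlation is a property of the data, and stronger correlation lowers the rate further. Both points stand, so the figures are illustrations and not bounds.

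Finally, the absence of adjustment is inferred from silence. A plan that is silent on adjustment nevertheless commits to none.

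**Conclusion.** The concern holds in a conditional form. The textual gap is certain: one threshold, up to 15 candidates per complication, unlisted complications, and no predictor criterion, multiplicity rule, exploratory label or validation.

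Its size is illustrative. If P ≤ 0.05 marks a predictor and no marker is informative, the per-complication chance of a false predictor is 54% (15 candidates) or 23% (five) under independence. It falls to about 17-18% (15, at 0.95/0.8) or about 10% (five, at 0.9). Several complications would raise the chance of at least one false predictor overall. AUCs and cut-offs for a selected marker would be too favourable, by about 0.13 to 0.17 on the AUC scale in the null settings tried at 0.5/0.2.

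The independent-test figures follow exactly from the plan's counts. The rest depends on assumed correlations and, for the AUC and cut-off results, on assumed numbers of patients and events. This should be fixed: the study remains analysable, but a claimed predictor could not be interpreted without these rules.

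**What to change.** List the complications and state how the three times enter the analysis. Then add to the Statistical analysis section:

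- All marker-time-complication results are exploratory and are reported with 95% CIs and the number of tests performed. Markers with P ≤ 0.05 are described as candidate predictors only.
- AUCs and cut-offs are reported with an optimism correction by repeated 5-fold cross-validation that repeats the marker, direction and cut-off selection in each resample. The bootstrap is a second choice, because it leaves about a third of the optimism in null simulation.
- Only if the sponsor wants a confirmatory claim, and the data have not been examined: name one complication, biomarker and time point as primary, tested at P ≤ 0.05, or apply Holm over the listed family.

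The cost is a little analysis work and no new data. Results lose confirmatory status, AUCs and cut-offs will look weaker, and cross-validated estimates are more variable. If a primary is named, a truly informative marker that was not chosen would be reported only as a candidate.

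### ROC analysis is used to identify predictors among 15 marker-time candidates per outcome in one cohort without internal validation, so accuracy quoted for anything singled out from those data will tend to be optimistic

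*Combined protocol and SAP*

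**What the plan says.** The Statistical analysis paragraph of the combined protocol and SAP plans "ROC-analysis to identify the predictors of postoperative complications". The same sentence goes on to odds ratios computed separately by dependent variable, which suggests more than one outcome.

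The marker list reads "The concentrations of proadrenomedullin, procalcitonin, presepsin, procalcitonin, troponin I and N-terminal brain natriuretic peptide measurement". Procalcitonin appears twice, so there are five distinct markers. The analyser sentence confirms this: two markers are run on the Kryptor, and the other three are "troponin I, NT-proBNP and presepsin on a PATHFAST analyzer". Samples are taken "before induction anesthesia, at the end of the surgical operation and in 6 hours after surgery".

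The Design line is "Single group assessment observational open label study", and the Objective is to "assess the association between levels of biomarkers and postoperative complications". The one stated decision threshold is "A P value ≤ 0.05 considered to be statistically significant".

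The text names no primary marker, sampling time or cut-off. It describes no bootstrap, cross-validation, split sample or second cohort, and gives no sample size, expected event count or target AUC.

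**The concern.** Using ROC analysis to identify predictors implies separating markers that predict from markers that do not, and the plan does not say how this will be done. The highest of 15 estimated AUCs is partly high by chance. So is a sensitivity and specificity pair read at a cut-off tuned on the same patients. If such figures are reported as they stand, a weak or useless marker can be presented as a predictor with an accuracy that new patients will not show.

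The concern reaches only the ROC results, and only what is singled out from them. The association analyses that serve the stated objective are not in question here.

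**Working it through.** **Inputs from the document.** Five distinct markers and three sampling times: 5 × 3 = 15 candidates per outcome. There is one cohort. The plan gives no ROC figure to reproduce.

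**Assumed inputs, because the document does not give them.** n = 50, 100 or 200 with 20% events (10, 20 or 40 events). Markers are normally distributed, with correlation 0.5 across times within a marker and 0.3 between markers. A true AUC of A corresponds to a mean shift δ = √2 × Φ⁻¹(A) between patients with and without a complication. Most settings used 4,000 simulated datasets.

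**No selection.** With all 15 AUCs reported, mean apparent minus true AUC lies between −0.001 and +0.001 in every setting.

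**Best of 15 singled out.** Optimism = mean apparent AUC of the selected candidate − its mean true AUC. Direction is fixed in advance except in the last row.

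| Assumed true AUCs | n = 50 | n = 100 | n = 200 |
|---|---|---|---|
| All 0.65 | 0.784 − 0.650 = 0.134 | 0.746 − 0.650 = 0.096 | 0.717 − 0.650 = 0.067 |
| One 0.70, rest 0.60 | 0.757 − 0.635 = 0.122 | 0.726 − 0.653 = 0.073 | 0.707 − 0.675 = 0.032 |
| Spread evenly 0.50 to 0.80 | 0.844 − 0.763 = 0.081 | 0.824 − 0.777 = 0.047 | 0.812 − 0.786 = 0.026 |
| One 0.80, rest 0.60 | 0.810 − 0.756 = 0.054 | 0.801 − 0.792 = 0.009 | 0.800 − 0.800 = 0.000 |
| All 0.50, direction chosen from data | 0.698 − 0.500 = 0.198 | 0.640 − 0.500 = 0.140 | 0.599 − 0.500 = 0.099 |

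**Sensitivity to the event rate (all true AUCs 0.65).** With 10% events the best-of-15 AUC averages 0.824/0.775/0.740, an optimism of 0.174/0.125/0.090. With 40% events it averages 0.762/0.729/0.706, an optimism of 0.112/0.079/0.056.

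**If only candidates with P ≤ 0.05 were singled out.** With 15 useless and independent candidates, the chance that at least one passes is 1 − 0.95¹⁵ = 0.537. Under the assumed correlations it is 0.442/0.434/0.440, and those that pass have a mean AUC of 0.737/0.668/0.619.

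**Cut-off only.** Take one pre-specified marker with true AUC 0.65, and choose the cut-off by maximising the Youden index (sensitivity + specificity − 1) on the same data. The best attainable value is 2Φ(δ/2) − 1 with δ = √2 × 0.385 = 0.545, which is 0.215. The in-sample index averages 0.364/0.318/0.284, against 0.183/0.190/0.197 in new patients. The optimism is 0.181/0.128/0.087, with no choice among markers at all.

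**The case against.** The strongest reply is that the harm depends on steps the plan does not state. The text mentions no best-marker rule, no cut-off, no sensitivity or specificity, and no clinical use of a threshold. The objective is association. If all 15 AUCs are reported, the selection bias does not arise. This stands, and it makes the point conditional. It does not remove it, because identifying predictors makes some selection plausible and nothing in the plan guards against its effect.

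The second reply is that the size is unknown and that equal true AUCs favour a large effect. This also stands. Spreading the true AUCs over 0.50 to 0.80 cuts the optimism to roughly 40% to 60% of the equal-AUC figures (0.026/0.067 = 39%; 0.081/0.134 = 60%). With one dominant marker it nearly vanishes from n = 100.

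Three stronger readings are tempting but unsupported:

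- A reader might infer that the plan commits to reporting an inflated best marker. It gives no selection rule, so this cannot be said.
- A reader might infer that P ≤ 0.05 is the rule for choosing ROC predictors. The threshold follows the sentence on the group-comparison tests and is not tied to the ROC analysis. The screening figures above only illustrate what would happen if it were used that way.
- A reader might infer that late sampling adds to the bias, because a complication could precede the sample said to predict it. That is a separate question of outcome definition. On the ordinary meaning of postoperative it reaches only the 6-hour sample, and no direction of bias follows from the text. It forms no part of this point.

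**Conclusion.** The point holds in conditional form: the plan invites selection among 15 candidates per outcome and provides no check on the optimism that selection brings. The direction is well supported, but the size is not determined by the document. Under the assumed 20% events and n = 50 to 200, optimism in a best-of-15 AUC with some true signal runs from about 0.13 down to zero. It depends on how far the true AUCs differ, and it shrinks as events accumulate. A cut-off chosen from the data adds optimism even for one pre-specified marker.

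This is a cheap improvement to reporting and analysis. It is not a defect that undermines the study's association objective.

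**What to change.** 1. For each complication outcome analysed, report all 15 AUCs with 95% confidence intervals, whatever their P values, and label them exploratory.
2. For any marker, time, direction or cut-off selected from the data, also report bootstrap optimism-corrected AUC, sensitivity and specificity. Repeat the whole selection in each resample.

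**Cost.** Item 1 is reporting only. Item 2 needs extra analysis code and will give less favourable accuracy figures. Neither needs more patients or samples.

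**Limits to state in the plan.** The correction is partial in small samples:

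- With 15 useless markers and n = 50, the corrected AUC averages 0.573 against a true 0.500 (apparent 0.699).
- With all true AUCs at 0.65 and n = 50, it averages 0.692 against 0.647 (apparent 0.784).
- For one pre-specified marker with true AUC 0.65 and n = 50, the corrected Youden index is 0.253 against 0.183 in new patients. So (0.253 − 0.183)/(0.364 − 0.183) = 39% of the optimism remains.
- For the best marker at its Youden cut-off (all true AUCs 0.65, n = 100), sensitivity is 0.761 apparent, 0.631 corrected and 0.557 in new patients.

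It can also over-correct slightly when one marker dominates: with one at 0.80, the rest at 0.60 and n = 100, it gives 0.776 against a true 0.791. Corrected figures should therefore be shown beside the apparent ones, with a note that some optimism may remain.
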